TITLE: Ultrasound guided posterior quadratus lumborum block for improved postoperative analgesia in minimally invasive gynecologic surgery

Date: June 19, 2020

TITLE

Ultrasound guided posterior quadratus lumborum block for improved postoperative analgesia in minimally invasive gynecologic surgery

INTRODUCTION

The overall decrease in morbidity associated with advances in minimally invasive surgery has transformed the concept of postoperative management, with lower complication rates, earlier mobilization, rapid postoperative recovery, and earlier discharge from the hospital. However, at times, laparoscopic surgery is associated with higher postoperative pain than traditional laparotomy in the immediate postoperative period; often requiring significantly higher doses of pain medication within the first 4 hours after surgery. In general, laparoscopic procedures could be associated with longer operative times; however, minimally invasive surgeons are presented with the most challenging patients- often morbidly obese, prior history of several surgical procedures in the abdomen and pelvis, and/or adhesive disease. Overall operative time is increased, including time under general anesthesia and amount of surgical dissection, which makes control of postoperative pain all the more problematic.

BACKGROUND AND SIGNIFICANCE

The challenge to achieve adequate analgesia has led to the development of directed, multi-modal protocols specific to management of post-laparoscopy pain in effort to decrease the amount of additional administration of narcotic medication. While several non-opioid regimens have been found to be effective, opioid medications still play a significant role in early postoperative analgesia. Given the adverse side effects of narcotic medications, regional blocks utilizing local anesthetic agents and has been shown to improve overall pain control in this time period.

Truncal abdominal nerve blocks are useful for pain control in abdominal and pelvic surgeries. More recently, the utilization of the quadratus lumborum (QL) block has effectively alleviated somatic and visceral pain in the upper and lower abdomen. The QL block provides analgesia spanning from the T4 to L1 dermatomal levels in the thoracolumbar plane to provide a broad sensory level analgesic effect. The approach involves injecting local anesthetic under ultrasound guidance into the plane posterior to the quadratus lumborum muscle and middle layer of thoracolumbar fascia.

Given the utility of the QL block in controlling somatic pain, this study aims to determine whether the QL block is an effective analgesic adjunct in the control of postoperative pain period, specifically with regards to patients undergoing laparoscopic gynecologic surgery.

STUDY OBJECTIVES

this study aims to determine whether the posterior QL blocks is an effective analgesic adjunct in the control of postoperative pain period, specifically with regards to patients undergoing laparoscopic gynecologic surgery.

HYPOTHESIS

The patients receiving QL blocks will have lower post-operative pain scores and will need less oral supplemental pain killers.

Subjects:

Women aged 18 to 65 presenting for scheduled laparoscopic or robotic total or supracervical hysterectomy for benign indication.

Eligibility Criteria:

Patient will be eligible for recruitment if between the ages of 18 to 65 scheduled to undergo laparoscopic or robotic total or supracervical hysterectomy for benign indications. Only surgery for benign pathology will be considered to enrollment. No Malignancy cases will be included.

Exclusion criteria:

1. History of adverse reaction or allergy to Bupivacaine or liposomal bupivacaine
2. Medical contraindication to placement of QL block.
3. Suspicion of possible reproductive cancer with contraindication of morcellation of uterine tissue.
4. Significant medical condition or laboratory result that in the opinion of the Investigator indicate an increased vulnerability to study subject which exposes the subject to an unreasonable risk as a result of participating.
5. Any clinically significant condition uncovered during the surgery, such as excessive bleeding or decompensation, that might render the subject medically unstable to continue the study or complicate the subject's intraoperative or postoperative course.

6. Pregnant patients
7. Less than 40Kg weight.

Design:

Prospective Cohort observational study. All patients that meet criteria for participation in this study will be screened: patients scheduled to undergo a laparoscopic hysterectomy for benign conditions by attending physicians in the division of Minimally Invasive Gynecologic Surgery. Based on surgeon's preference, and patient's consent, the patient is offered a QL block or not. Our aim is to follow the patient's pain scores post op and amount of oral pain medication used whether they received QL block or not. If the patient received the QL block then they will be considered part of the study arm. If the patient did not receive the QL block then they will be considered part of the control arm.

The QL block is best thought of as a volume or compartment block in that volumetric spread of LA along the fascial plane is associated with efficacy in blocking the thoracolumbar nerves between T7-L1. It can be reasonably assumed that this compartment is the same across patients and is not affected by the amount of subcutaneous or central fat present in the obese patient.

If a block is to be performed, the QL block will be performed using a 21G x 100mm Stimuplex needle under ultrasound guidance using a curvilinear probe. Subjects will be positioned in the semi-lateral position to facilitate access into the plane posterior to the quadratus lumborum muscle and middle layer of thoracolumbar fascia. The QL block will be administered via an in-plane approach and local anesthetic will be injected between the quadratus lumborum muscle and the middle layer of the thoracolumbar. The QL block will be in the operating room after induction prior to starting the scheduled surgical procedure. If the block is performed, it will include 20ml of 0.25% bupivacaine and 5ml of liposomal bupivacaine (Exparel) per side. The block will be done bilaterally therefore **a total** of 40ml of 0.25% bupivacaine and 10ml of liposomal bupivacaine (Exparel) will be administered.

Patients will be pre-medicated with Midazolam. Routine monitoring will be performed including electro-cardiography, non-invasive blood pressure monitoring, heart rate oxygen saturation and end-tidal carbon dioxide and capnograph will be performed. General anesthesia will be induced with Propofol 1-2 mg/kg and analgesia will be provided with Fentanyl 2 mcg/kg. General anesthesia will be maintained using the Sevoflurane titrated to effect as determined by the anesthesia team caring for the patient. Rocuronium will be administered during the duration of the case to provide muscle relaxation for the duration of the procedure, with an induction dose of 0.6 mg/kg and titrated to 1-2 twitches assessed by continuous twitch monitor. Reversal of neuromuscular blockade will be achieved using 0.06 mg/kg of Neostigmine and 0.012mg/kg of Glycopyrrolate or 2mg/kg of sugammadex.

Possible allergic type reactions of receiving bupivacaine include urticaria, pruritis, erythema, angioedema, tachycardia, sneezing, nausea, vomiting, dizziness, and syncope. Overdosage or rapid absorption lead to systemic toxicity manifestation that need immediate counter measures related to the central nervous system and cardiovascular system. There is also risk of nerve injury given the location of the regional block. Routine precaution is taken by the surgical and anesthesia team to avoid overdosing. Any reactions or overdosing will be managed accordingly. The study will not alter the subjection to possible adverse reaction as this is an observational study.

Data Collection Procedures:

As this is an observational (prospective cohort) study, there will be no randomization or blinding done. We will be observing the patient's post op pain scores and amount of pain medication used

Postoperatively, patients will be transferred to the PACU for monitoring. The amount, timing and type of additional pain medications necessary at 1 and 3 hours after surgery will be recorded. Pain levels will be documented at the same 1- and 3-hours intervals, and scored utilizing a 1-10 Numeric Rating Scale (NRS). The NRS is a verbal assessment, asking patients to quantify their pain on 1- 10 scale. It has previously been shown in studies to be a simple, valid alternative to the visual analog scale (VAS).

Study subjects will receive a telephone call 24 hours after surgery and asked about how much additional medication they have taken for pain control, as well as their pain level utilizing the same 1-10 NRS assessment.

Our primary outcome is difference in pain scores at 3 hours. Our secondary outcome is difference in pain scores, at 1 hour, 24 hours, difference in additional medication taken orally for pain control, and adverse effects if any.

Sociodemographic and clinical data of study subjects will also be obtained, including age, body mass index, history of abdominal and pelvic surgeries, history of pelvic adhesive diseases such as endometriosis, duration of surgery, and duration of stay postoperatively in PACU.

Data Analysis: the mean difference between pain scores at 1 hour, 3 hour, and 24 hour, and the difference in the amount of oral pain medication used will be assessed as below.

Expected Outcomes: Our study aims to show that patients receiving a preoperative QL block will have lower post-operative pain scores and will need less oral pain medication

REFERENCES:

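### Exclusion criterion 5 acts after the block has been given or withheld, so serious intraoperative reactions to the block may be dropped before adverse effects are compared

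*Combined protocol and SAP*

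**What the plan says.** All references are to the combined protocol and SAP.

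- **Exclusion criteria, item 5.** Patients are excluded for "Any clinically significant condition uncovered during the surgery, such as excessive bleeding or decompensation". The rule applies where such a finding could leave the patient too unstable to remain in the study, or could make her course during or after the operation more difficult. The other six items can be judged before surgery.
- **Design, timing and arms.** Arms are defined by whether the block was received. On timing: "The QL block will be in the operating room after induction prior to starting the scheduled surgical procedure".
- **Design, risks.** The plan anticipates serious drug reactions: "Overdosage or rapid absorption lead to systemic toxicity manifestation that need immediate counter measures related to the central nervous system and cardiovascular system". It adds: "The study will not alter the subjection to possible adverse reaction as this is an observational study".
- **Data Collection Procedures.** The plan states that "there will be no randomization or blinding done". The secondary outcomes end with "difference in additional medication taken orally for pain control, and adverse effects if any". Follow-up extends past the recovery room: "Study subjects will receive a telephone call 24 hours after surgery".

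No section says whether patients who meet item 5 stay in any analysis, are followed, or are reported by arm. No safety population is defined. The plan does not say who applies item 5.

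**The concern.** An exclusion rule that depends on what happens after exposure can remove the outcomes the study is meant to compare. Item 5 is such a rule. It names decompensation, it extends to anything that may complicate the patient's course, and it does not exempt events caused by the block.

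The difference in adverse effects is biased when the share of patients removed with an event differs between arms. Block toxicity can arise only in the block arm, and whoever applies item 5 may know which arm the patient is in. The events most likely to be lost are the serious ones, so the bias from this source favors the block.

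The pain comparison is also restricted to patients who pass a post-exposure filter, but that is a lesser matter.

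**Working it through.** **Order of events.** (1) Induction. (2) Block given or not, which fixes the arm. (3) Surgery starts. (4) Item 5 can now be triggered. (5) Pain and medication at 1, 3 and 24 hours; adverse effects compared. Item 5 therefore falls between exposure and outcome.

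**What item 5 can and cannot catch.** Serious toxicity appearing during surgery fits the wording. A reaction before surgery starts arguably does not. Milder or postoperative effects, such as itching, nausea or nerve injury, would still be counted.

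**Inputs.** The plan states no event rate, sample size or exclusion rate, so there is no figure of its own to reproduce. Every rate below is assumed, for illustration.

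**A. Block-only serious events on top of milder effects (closest to the mechanism).** Milder effects are 5% in both arms; serious intraoperative events are 1% in the block arm only. A fraction f of the serious cases is removed. Observed block risk = (0.06 − 0.01f)/(1 − 0.01f); control stays at 5.00%.

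| f | Block | Difference (points) | Risk ratio |
|---|---|---|---|
| 0 | 6.00% | 1.00 | 1.20 |
| 0.5 | 0.055/0.995 = 5.53% | 0.53 | 1.11 |
| 1 | 0.05/0.99 = 5.05% | 0.05 | 1.01 |

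Varying the serious rate with no other events in either arm: for rates of 0.5%, 1% and 3%, removing half leaves differences of 0.25, 0.50 and 1.52 points, and removing all leaves 0.

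**B. Same fraction f of all event patients removed in each arm.** Observed risk = p(1 − f)/(1 − pf), with true risks of 2% (block) and 1% (control).

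- f = 0.25: 1.508 − 0.752 = 0.76 points
- f = 0.5: 1.010 − 0.503 = 0.51 points
- f = 1: 0 points, a limiting bound only

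**C. Equal share q of each arm removed as event patients.** Difference = (p1 − p0)/(1 − q). With 5% against 2% and q = 1%: 0.03/0.99 = 3.03 points, against a true 3.00. There is essentially no bias here.

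**D. 3-hour pain.** If removed patients would score e NRS points above retained ones in both arms, the shift in (block − control) is −(share removed in block − share removed in control) × e.

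- 8% against 3%, e = 2: −0.05 × 2 = −0.10; shares reversed, +0.10
- 10% against 3%, e = 3: −0.07 × 3 = −0.21; shares reversed, +0.21
- 5% against 5%, e = 2: 0

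**The case against.** The strongest reply is that item 5 was never meant for drug reactions. A condition uncovered at surgery, with bleeding as the first example, most naturally means a surgical or patient finding, and the plan discusses block reactions elsewhere without linking them to item 5. Instability might also mean only that follow-up stops, with data already recorded being kept. This reading is possible, but the text does not state it. Decompensation is an event that develops, block-related causes are not exempted, and the rule stands among the exclusion criteria.

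Several narrower points do stand:

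- The window is limited to serious reactions that first appear during surgery and are classified under item 5.
- Calculation B removes event types that item 5 would mostly not catch, and it nearly keeps the risk ratio (1.508/0.752 and 1.010/0.503 are both about 2.0, as is 2%/1%). Calculation A carries the argument, and there the ratio shrinks too.
- The 1% serious rate in A has no support in the documents. Bleeding and similar surgical events may be removed equally from both arms, as in C.
- Adverse effects are the last-listed secondary outcome; the hypothesis and the Data Analysis paragraph concern pain and medication. With no sample size stated, it is unknown how informative a serious-event comparison would be even with everyone kept.
- The NRS is given verbally, so an unstable patient may be unable to supply a score. That justifies a missing value, not removal of the patient from the adverse-effects count.

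**Conclusion.** The concern holds. As written, item 5 operates after exposure and is broad enough to remove serious intraoperative reactions to the block from a comparison in which they are an outcome. For those events the bias favors the block.

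The size cannot be determined from the documents. Under the assumptions in A, a true 1.0-point excess falls to 0.53 points with half the serious cases removed and to 0.05 with all removed, even though milder effects are fully counted. If equal shares of both arms are removed as event patients, the difference is essentially unchanged. The effect on 3-hour pain is probably small, about 0.10 to 0.21 NRS points in either direction under the assumed imbalances and zero without imbalance.

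The conclusion rests on intraoperative toxicity being classed under item 5, which the text permits but does not require. The rule should be changed, but the point does not undermine the primary pain comparison.

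**What to change.** Stop using item 5 to remove patients from the analysis.

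- Define the cohort by criteria known before the block is given or withheld, and count every such patient in the adverse-effects comparison.
- Report item 5 cases and intraoperative complications by arm, with reasons.
- Keep these patients in the pain and medication analyses wherever data are obtained, including the 24-hour call. Record a score that cannot be obtained as missing, with the reason.
- Omit item 5 cases only in a labelled sensitivity analysis.

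The cost is one or two sentences in the eligibility and analysis text and one extra by-arm table. A few atypical cases will add some variance to the pain scores, and some will lack a 1- or 3-hour score, so the gain is mainly in the adverse-effects comparison. The study is observational, so keeping these patients in the analysis changes nothing in their clinical management.

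### The screening sentence leaves it unclear whether robotic cases and other surgeons' patients enter the cohort, and route and extent of hysterectomy are neither listed for collection nor adjusted for

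*Combined protocol and SAP*

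**What the plan says.** **Who is eligible.** Subjects reads "Women aged 18 to 65 presenting for scheduled laparoscopic or robotic total or supracervical hysterectomy for benign indication". Eligibility Criteria repeats this as "scheduled to undergo laparoscopic or robotic total or supracervical hysterectomy for benign indications". Neither limits enrolment to a division or a group of surgeons.

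**Who is screened.** The sentence in Design opens "All patients that meet criteria for participation in this study will be screened" and then, after a colon, spells those patients out as "patients scheduled to undergo a laparoscopic hysterectomy for benign conditions by attending physicians in the division of Minimally Invasive Gynecologic Surgery".

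**What the study is about.** The title refers to "improved postoperative analgesia in minimally invasive gynecologic surgery". Study Objectives is worded "specifically with regards to patients undergoing laparoscopic gynecologic surgery".

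**What is recorded.** Data Collection Procedures states "Sociodemographic and clinical data of study subjects will also be obtained, including age, body mass index, history of abdominal and pelvic surgeries", and the list goes on with "history of pelvic adhesive diseases such as endometriosis, duration of surgery, and duration of stay postoperatively in PACU". Route and extent of hysterectomy, concomitant procedures and conversion to laparotomy are not named.

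**How the arms are formed and compared.** Under Design, the block is offered according to the surgeon's preference and the patient's consent. Data Collection Procedures confirms that there is no randomization or blinding. The primary outcome is the difference in pain scores at 3 hours; Data Analysis refers to mean differences and mentions no adjustment.

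**The concern.** Staff who apply Eligibility would screen a robotic case, and staff who apply the words after the colon in Design might not. The same holds for an eligible patient whose surgeon is outside the named division. The protocol does not say which text governs.

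This matters more here than in a randomized trial. The surgeon's preference helps decide the block, and the surgeon plausibly also influences route and extent. If either is related to early pain, part of the difference at 3 hours would reflect the operation and not the block. The Introduction gives some reason to take this seriously: it contrasts early pain after laparoscopy and laparotomy, and it links operative time and the amount of dissection to harder pain control. It does not say that robotic differs from laparoscopic, or total from supracervical, so these are possible confounders and not established ones.

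**Working it through.** The documents state no sample size, target difference or standard deviation, so there is no figure of the plan's own to reproduce. The check is a comparison of texts, followed by an illustration on assumed inputs.

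**Step 1. Population wording side by side.**

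| Place | Procedure | Route | Surgeon |
|---|---|---|---|
| Study Objectives | gynecologic surgery, not limited to hysterectomy | laparoscopic | not limited |
| Subjects; Eligibility Criteria | benign hysterectomy, total or supracervical | laparoscopic or robotic | not limited |
| Design, after the colon | benign hysterectomy, extent not stated | laparoscopic | one division's attending physicians |

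Between Eligibility and Design, two differences bear on who enters: robotic cases and the surgeon restriction. Leaving extent unstated in Design excludes nobody.

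**Step 2. What each reading implies for confounding.**
- Eligibility governs: route and extent can both differ between arms.
- Design is applied literally to everyone: robotic cases are absent from both arms and route cannot confound. Extent still can.
- The two are applied unevenly: both can differ, and entry also depends on who does the screening.

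Extent is therefore a possible confounder under every reading, and route under two of the three.

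**Step 3. Can the planned data and analysis deal with it?** The named items are age, body mass index, surgical history, adhesive disease, duration of surgery and PACU stay. Route and extent do not appear among them. Duration of surgery does not identify the procedure. It also arises after the block, which Design places between induction and the start of surgery. No adjusted comparison is described.

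**Step 4. Illustration only.** With an additive effect on the mean score, spurious difference = (difference between arms in the share of patients with the feature) × (effect of the feature on the 3-hour score). Assume an imbalance of 20 to 40 percentage points and an effect of 0.5 to 1 point; none of these values comes from the documents.
- 0.20 × 0.5 = 0.10
- 0.20 × 1.0 = 0.20
- 0.40 × 0.5 = 0.20
- 0.40 × 1.0 = 0.40

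The result is 0.1 to 0.4 points on the 1-10 scale, in either direction. With no imbalance or no effect it is zero.

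**The case against.** The strongest reply is that the screening sentence begins by referring back to the eligibility criteria, so the words after the colon may be shorthand, with laparoscopic used loosely to include robot-assisted cases. That is a fair reading, and a reader who infers three truly different study populations goes further than the text. What stands is that Subjects and Eligibility both name robotic as an alternative to laparoscopic, and that the division restriction is not explained by loose terminology.

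Other stronger readings are tempting and should not be adopted:
- **That sites or surgeons will screen differently.** The documents name no second site and refer to one division. Uneven screening is a risk of the wording; nothing shows that it will happen.
- **That route and extent are not collected and the bias could never be removed.** The list is introduced by including, so it is open, and the operative record can be expected to hold these facts. The supportable statement is that they are not listed for collection.
- **That every converted patient stays in, unidentified.** Eligibility does turn on the scheduled procedure, but exclusion criterion 5 removes patients with clinically significant conditions found during surgery and may catch some conversions. It does not mention conversion, so it cannot be relied on to catch all.
- **That the study will draw too broad a conclusion.** The protocol contains no conclusion, and a general objective made specific by eligibility criteria is ordinary drafting. This is mainly a matter of wording.

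It is also fair to say that the larger problem is surgeon-chosen allocation without specified adjustment, and that route and extent are two covariates within it. That limits the weight of this point but does not remove the gap.

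**Conclusion.** The point holds as an ambiguity in screening combined with a gap in the planned covariates. The text does not settle whether robotic cases and patients of surgeons outside the division are screened. Two plausible determinants of both block use and early pain would, as the plan is written, be neither shown by arm nor adjusted for.

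The size of any bias is unknown from the documents. The 0.1 to 0.4 point range rests wholly on assumption, and its upper end needs a large imbalance and a full 1-point effect together. Nor is there a target difference or standard deviation to judge it against. The case for acting rests on the low cost and the non-randomized comparison, not on a demonstrated bias. It is best settled before enrolment: route and extent can be recovered later from records, but the 3-hour scores of eligible patients who were never screened may not be.

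**What to change.** 1. **Reconcile the screening sentence in Design with Eligibility Criteria.** State explicitly whether robotic cases are screened and whether patients of surgeons outside the division are screened, and use that one definition throughout.
2. **Add scheduled route (laparoscopic or robotic) and scheduled extent (total or supracervical)** to the list in Data Collection Procedures, taken from the operative record. Report both by arm. Include them in an adjusted comparison of 3-hour pain scores with the other pre-block covariates; of those already listed, these are age, body mass index, surgical history and history of adhesive disease. Duration of surgery and PACU stay arise after the block and do not belong in that set.
3. **Record concomitant procedures and conversion to laparotomy and report them by arm.** Do not adjust for conversion, because it occurs after the block.
4. **Word the conclusion for the population enrolled:** benign laparoscopic or robotic hysterectomy, in line with the definition settled in item 1.

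The cost is a wording amendment, a few fields from existing records, one adjusted analysis to specify, and a slightly narrower conclusion. No treatment changes and no extra patient contact are needed.

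### Surgeon's preference helps decide who is offered the block, but the operating surgeon is not among the listed data and no analysis accounts for surgeon, so an ordinary two-group interval may be too narrow.

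*Combined protocol and SAP*

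**What the plan says.** The Design section recruits patients who are to be operated on "by attending physicians in the division of Minimally Invasive Gynecologic Surgery", so more than one surgeon takes part; the number is not given. On who gets the block it says: "Based on surgeon's preference, and patient's consent, the patient is offered a QL block or not". The arm then follows the treatment received: "If the patient received the QL block then they will be considered part of the study arm". Data Collection Procedures confirms that "there will be no randomization or blinding done".

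The same section sets the endpoint: "Our primary outcome is difference in pain scores at 3 hours". It then lists the background data: "Sociodemographic and clinical data of study subjects will also be obtained, including age, body mass index, history of abdominal and pelvic surgeries", followed by "history of pelvic adhesive diseases such as endometriosis, duration of surgery, and duration of stay postoperatively in PACU". The operating surgeon is not named, although the list is worded as examples and need not be complete.

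Data Analysis names "the mean difference between pain scores at 1 hour, 3 hour, and 24 hour" and the difference in oral pain medication. It refers forward to a method, but the next text is Expected Outcomes and then the references. No test, interval, model, adjustment or surgeon term is stated.

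**The concern.** Surgeon's preference is one of two stated drivers of the arm. If it is partly a habit that differs between surgeons, patients of one surgeon will tend to fall in the same arm. They also share that surgeon's technique and perioperative routine, which can shift their pain scores together.

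Two things follow. First, a simple difference in means then contains differences between surgeons as well as any effect of the block. Second, an ordinary two-group interval counts each patient as independent information. A shared surgeon effect does not average out as one surgeon contributes more patients, so the true standard error exceeds the calculated one. Adjusting for the listed patient characteristics would not remove the part of the surgeon effect that they do not explain.

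The 3-hour primary outcome is at stake, and likewise the 1-hour, 24-hour and medication comparisons. With few surgeons, a chance difference between them could be reported as an effect of the block.

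**Working it through.** **There is no figure in the plan to reproduce.** The documents give no sample size, standard deviation, significance level, number of surgeons, patients per surgeon, ICC or split of block use. Everything below is illustration under assumptions.

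**Assumptions.** Each surgeon operates on m = 20 patients. Half the surgeons favour the block and half do not, and each patient's treatment follows the surgeon's preference with probability p. Scores share a random surgeon effect with ICC ρ = 0.02, 0.05 or 0.10. The block has no true effect.

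**Formulas.** For the simple mean difference, true variance divided by the variance calculated under independence is approximately

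R = 1 + (m − 1) × ρ × (2p − 1)².

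The standard error is too small by a factor √R, and a nominal two-sided 5% test rejects with probability 2 × P(Z > 1.96/√R).

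**Example.** At p = 0.9 and ρ = 0.05, (2 × 0.9 − 1)² = 0.64, so R = 1 + 19 × 0.05 × 0.64 = 1.608 and √R = 1.27. Then 1.96/1.268 = 1.546, giving 12.2%.

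| Preference followed (p) | √R at ρ = 0.02 / 0.05 / 0.10 | Rejection rate, nominal 5% |
|---|---|---|
| 100% | 1.17 / 1.40 / 1.70 | 9.5% / 16.0% / 25.0% |
| 90% | 1.11 / 1.27 / 1.49 | 7.9% / 12.2% / 18.8% |
| 70% | 1.03 / 1.07 / 1.14 | 5.7% / 6.8% / 8.6% |
| 50% | 1.00 / 1.00 / 1.00 | 5.0% / 5.0% / 5.0% |

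Simulation with 6 surgeons and a score SD of 2 agrees: 9.6% / 15.6% / 25.5% at full preference, 7.3% / 12.9% / 19.4% at 90%, and 5.7% / 6.7% / 8.4% at 70%.

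**Sensitivity to patients per surgeon.** At full preference R = 1 + (m − 1)ρ. For m from 5 to 20 and ρ from 0.01 to 0.10, R runs from 1.04 to 2.90, and coverage of a nominal 95% interval from 94.5% down to 75.0%. With m = 10 and ρ = 0.05, R = 1.45 and coverage is 89.6%.

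**Sensitivity to how treatment is split.** If each surgeon treated an exact share p of patients, the ratio would be 1 − ρ + ρm(2p − 1)². At an exact 50/50 split this is 0.90 to 0.99, so the simple interval would be slightly too wide (coverage 95.1% to 96.1%). The break-even share is p = 0.5 + 0.5/√m: 0.72, 0.66 and 0.61 for m = 5, 10 and 20.

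**Surgeon-adjusted comparison.** With surgeon as a fixed effect, simulated rejection rates were about 4% to 5.6% where the model can be estimated. It cannot be estimated when every surgeon uses only one option. For 6 surgeons, SD 2 and ρ = 0.05, the SD of the estimate goes from about 0.47 points (simple) to 0.62–0.64 (adjusted) at 90% preference, and from 0.39 to 0.40 at 70%.

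**Few surgeons.** With 6 surgeons and all-or-none use, inference rests on 6 − 2 = 4 degrees of freedom. The critical value is 2.78, against 1.96.

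**The case against.** The strongest reply is that the plan contains no interval or test to be wrong. A mean difference is only a point estimate and assumes nothing about independence; the documented gap is the missing method. This stands, and the point is therefore about the ordinary two-group analysis that a bare mean difference invites.

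A reader might also infer that the surgeon largely sets the arm. The text does not support that. It names the patient's consent beside the surgeon's preference, gives no split, and does not say whether preference is a fixed habit or a case-by-case judgement. If each surgeon used the block in about half of patients, there would be no inflation.

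Nor can one conclude that surgeon will be unavailable at analysis. The data list is not worded as exhaustive, and the operating surgeon might be recoverable from operative records. What can be said is that the listed data do not allow surgeon to be handled.

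It may further be said that this is confounding under another name. That is partly right: with a small fixed group of surgeons, a surgeon effect aligned with the arm is a bias, and a wider interval alone would not remove it. That argues for a within-surgeon comparison, not against recording surgeon.

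Finally, the fixed-effect remedy fails at full preference, where the inflation is largest. This also stands, which is why a fallback has to be specified in advance.

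**Conclusion.** The point holds in conditional form. Three facts come from the documents: preference is a stated driver of the arm among several surgeons, the operating surgeon is not listed, and no analysis step accounts for surgeon. That the simple interval would be too narrow is a consequence only if block use differs by surgeon and scores correlate within surgeon. The documents establish neither, so it should not be stated as a fact about this study.

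The plausible size runs from nothing, with even use within surgeons, to a false-positive rate of about 25% with all-or-none use, ICC 0.10 and 20 patients per surgeon. Only block use tabulated by surgeon can show where this study lies in that range, and the listed data do not permit that table. The change is worth making because it is cheap and the analysis method has still to be written.

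**What to change.** 1. Add a coded operating-surgeon field to the background data listed under Data Collection Procedures.
2. Report block use by surgeon, including how many surgeons used both options.
3. In Data Analysis, make the primary 3-hour estimate surgeon-adjusted, with surgeon as a fixed effect, and report its interval as the main result. State that only surgeons with patients in both arms inform it. Treat the 1-hour, 24-hour and medication comparisons in the same way.
4. Specify the fallback now: if fewer than a stated number of surgeons use both options, with that threshold set before outcomes are seen, use a random surgeon intercept with degrees of freedom based on the number of surgeons. Say that surgeon and block effects then cannot be cleanly separated, and that the conclusion rests on the number of surgeons more than on the number of patients.

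The cost is one coded field, one table and a few sentences of analysis text. The statistical price is a wider interval when preference is strong and almost none when it is moderate, as the SDs in the working show.
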